
10.1.2 Changes From Baseline in Overall EASI Score and EASI Symptom Scores

Based on the OC data set, the change from baseline in EASI score (at Week 1, Week 2, and Week 4; if the timing of discontinuation falls within the allowable window of a timepoint, the data at discontinuation will be included as the data for the timepoint) will be analyzed using the MMRM analysis with treatment (0.3% or 1% OPA-15406 group, and vehicle group), timepoint, and interaction between treatment and timepoint as factors and baseline EASI score as a covariate. An unstructured covariance matrix will be used to model the within-subject errors and Kenward-Roger method will be used to calculate the standard error of fixed-effects and the degree of freedom. If the MMRM procedure fails to converge under unstructured covariance structure, the following structure will be used in the order of 1) heterogeneous toeplitz, 2) heterogeneous autoregressive of order 1, 3) heterogeneous compound symmetry and the first (co)variance structure converging to the best fit will be used.

The least square mean of each treatment group will be calculated by timepoint. For overall EASI score, the least square mean and the standard error will be plotted by timepoint for each treatment group. The difference in the least square mean between the vehicle group and each OPA-15406 group, and the two-sided 95% confidence interval and p-value will be calculated at Week 1, Week 2, and Week 4.

Based on the OC and LOCF data sets, ANCOVA model with treatment (0.3% or 1% OPA-15406 group, and vehicle group) as a factor and baseline EASI score as a covariate will be applied to the change from baseline up to each timepoint. The least square mean in each treatment group will be calculated by timepoint. The difference in the least square

mean between the vehicle group and each OPA-15406 group, and the two-sided 95% confidence interval and p-value will be calculated at Week 1, Week 2, and Week 4. Based on the OC and LOCF data sets, measured values and changes from baseline in IGA at Week 1, Week 2, and Week 4 will be summarized by treatment group using descriptive statistics. For the overall EASI score, the mean with standard error of measured values (in the OC and LOCF data sets) will be plotted by timepoint for each treatment group.

EASI scores for body regions (face, neck, and head; upper limbs; trunk; and lower limbs) will be analyzed in the same manner as the overall EASI score.

10.1.3 Change From Baseline in Visual Analogue Scale for Pruritus

The change from baseline in visual analogue scale (VAS) for pruritus will be analyzed in the same manner as that in the overall EASI score or each EASI symptom score.

10.1.4 Change From Baseline in VRS for Pruritus up to Day 7

The change from baseline in VRS score for pruritus up to Day 7 will be analyzed in the same manner as that in overall EASI score or each EASI symptom score. Data will be collected at baseline, 4, 8, and 12 hours after the start of administration, 1 day after the start of administration (morning and night), and thereafter in the same manner up to Day 7 (morning). The same analysis will be performed by the time zone of assessment (morning or evening). Morning or evening will be determined based on the time label entered in the case report form (CRF), not using the timepoints defined in Table 6.4-2, except the baseline, which is irrespective of the time zone of assessment. Data will be collected at baseline, and the timepoints specified above on Day 1 to Day 7.

10.1.5 Change From Baseline in Patient-Oriented Eczema Measure Score

The change from baseline in Patient-Oriented Eczema Measure (POEM) score will be analyzed in the same manner as that in the overall EASI score or each EASI symptom score.

10.1.6 Change From Baseline in Overall Percentage Affected BSA

The change from baseline in overall percentage affected BSA will be analyzed in the same manner as that in the overall EASI score or each EASI symptom score.

10.1.7 Percent Changes From Baseline in Overall EASI Score, EASI Symptom Scores, VAS for Pruritus, and POEM Scores

The percent changes from baseline in overall EASI score, EASI symptom scores, EASI scores for body regions, VAS for pruritus, and POEM score will be analyzed in the same manner as the changes from baseline in the respective scores.

10.1.8 Time to Response in IGA

For the time to response in IGA (days to the first response in IGA in each subject), a cumulative response rate will be computed by treatment group using the Kaplan-Meier method and plotted. At each timepoint, the number of subjects (at risk), the p-value of the log-rank test comparing the vehicle group and each OPA-15406 group, and the time until one half of the subjects have achieved a response (medial survival time [MST]) will be provided. Subjects with an IGA of 0 (clear) or 1 (almost clear) with an improvement by at least 2 grades from the baseline are defined as responders. The starting point is the baseline. Subjects who have failed to achieve a response will be treated as censored on the day of the final IGA assessment.

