- 5) Change from baseline in VRS for pruritus up to Day 7 will be calculated. Using the OC and LOCF data sets up to Day 7, ANCOVA with factors of treatment (0.3% or 1% OPA-15406 groups, vehicle group), and baseline value will be applied to the change from baseline up to each timepoint based on OC and LOCF dataset. The least square mean of each treatment group will be calculated by timepoint. Also, the difference in the least square means between the vehicle group and each OPA-15406 group, and the two-sided 95% confidence interval and p-value will be calculated. Using the OC and LOCF data sets, the descriptive statistics will be calculated for measured values and changes from baseline by treatment group for each timepoint. The data will be collected at 4, 8, and 12 hours after the start of administration, 1 day after the start of administration (morning and night), and thereafter in the same manner up to Day 7 (morning).
- 6) For time to response in IGA and VRS for pruritus, Kaplan-Meier plots will be generated for each treatment group and vehicle group. For IGA, subjects with an IGA score is 0 (clear) or 1 (almost clear) with an improvement by at least 2 grades

from the baseline are defined as responders. For VRS for pruritus, subjects with VRS score of 0 (none) or 1 (mild) with an improvement by at least 1 grade from the baseline are defined as responders.

- 7) The descriptive statistics (number of subjects, arithmetic mean, standard deviation, coefficient of variation, minimum value, median value, and maximum value) of plasma OPA-15406 concentrations will be calculated by treatment group and by timepoint.
- 8) The descriptive statistics (number of subjects, arithmetic mean, standard deviation, coefficient of variation, minimum value, median value, and maximum value) of plasma OPA-15406 concentrations adjusted for affected area (%) per total BSA at baseline evaluation will be calculated by treatment group and by timepoint.
- 9) The descriptive statistics (number of subjects, arithmetic mean, standard deviation, coefficient of variation, minimum value, median value, and maximum value) of plasma OPA-15406 concentrations will be calculated by treatment group, by timepoint, and by affected area per total BSA at baseline examination (5% to <10%, ≥10% to <30%, and ≥30%).

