6.3 Data Conversion and Calculation

6.3.1 Response in Investigator's Global Assessment

Responders and non-responders in investigator's global assessment (IGA) are defined as follows:

- 1) Primary analysis for incidence of success in IGA
 - Subjects with an IGA score of 0 (clear) or 1 (almost clear) with an improvement by at least 2 grades from baseline are defined as responders. Subjects with missing IGA data at the time of evaluation will be handled as non-responders.

- 2) Sensitivity analysis
 - Subjects with an IGA score of 0 (clear) or 1 (almost clear) with an improvement by at least 2 grades from baseline are defined as responders. For subjects with missing IGA data at the time of evaluation, the last observation carried forward (LOCF) will be used.
 - Subjects with an IGA score of 0 (clear) or 1 (almost clear) with an improvement by at least 2 grades from baseline are defined as responders. Observed cases (OC) will be used.

- Subjects with an improvement in IGA score to 0 (clear) or 1 (almost clear) are defined as responders. Subjects with missing IGA data at the time of evaluation will be handled as non-responders.

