6.5 Handling of Missing Values

Missing data for incidence of success in IGA will be handled as described in “[Section 6.3.1 Response in Investigator’s Global Assessment.](#)” Other variables at each timepoint will be analyzed based on the OC and LOCF data sets.

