10.1.9 Time to Response in VRS

The time to response in VRS (time to the first response in VRS in each subject) will be analyzed in the same manner as the time to response in IGA. Subjects with a VRS score of 0 (none) or 1 (mild) with an improvement by at least 1 grade from the baseline are defined as responders. The starting point is baseline. Subjects who have failed to achieve a response will be treated as censored on the day of the final VRS assessment.

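### Time to IGA response (SAP 10.1.8) runs on actual days with censoring at the last IGA, so scatter in Week 4 visit dates inflates the Kaplan-Meier response curve

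*SAP*

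**What the plan says.** SAP 10.1.8 defines the variable as "days to the first response in IGA in each subject", starting from baseline, and plans that "a cumulative response rate will be computed by treatment group using the Kaplan-Meier method and plotted". It also asks for the number at risk at each timepoint, log-rank p-values of each active group against vehicle, and the time until half the subjects have responded. One censoring rule covers all non-responders, whether withdrawn or finished: "Subjects who have failed to achieve a response will be treated as censored on the day of the final IGA assessment".

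Protocol 7.4.2 item 6 is the source of the analysis and gives no censoring rule: "For time to response in IGA and VRS for pruritus, Kaplan-Meier plots will be generated for each treatment group and vehicle group".

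The Protocol's schedule of assessments allows ±2 days at Week 1 and ±3 days at Weeks 2 and 4. SAP Table 6.4-1 assigns data to Week 1, 2 or 4 (study days 8, 15, 29; the Week 4 window is Days 22 to 43). Neither SAP 6.4 nor 10.1.8 says that these nominal days replace the actual days in the time-to-response analysis.

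For the success rate, SAP 6.3.1 says: "Subjects with missing IGA data at the time of evaluation will be handled as non-responders". SAP 6.5 sets the scope of that rule: "Missing data for incidence of success in IGA will be handled as described in" 6.3.1, while "Other variables at each timepoint will be analyzed based on the OC and LOCF data sets".

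**The concern.** IGA is assessed at only three scheduled post-baseline visits. A child seen without response on Day 27 and a child seen with response on Day 31 have both had their Week 4 assessment. On an actual-day scale the first child is removed on Day 27, and the second child's response is divided by the few children whose visits fell on Day 31 or later. The estimator treats the first child as still able to respond on Days 28 to 31, although no further IGA is planned for that child. The excess comes from appointment dates, not from efficacy.

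Readers will take a cumulative response rate and a time to half responding at face value. In a dose-response trial with 20 children per arm, a curve well above the share who responded could mislead about the size of the effect, and a median could be reported when fewer than half responded.

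**Working it through.** **Plan's own figures.** The plan gives no figure for the time-to-response analysis. The response rates used below are those of SAP 12.2 (20.93%, 14.63%, 2.7%; 20 per arm). Exact enumeration of independent Binomial(20, p) counts gives 95.5%, 86.9%, 71.5% and 58.9% for the four probabilities in SAP 12.2, against the stated 96.2%, 88.3%, 71.5% and 60.6%. All agree within 2 points, so the inputs are read as intended.

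**Formula.** The cumulative response is 1 − Π(1 − d/n), taken over the days with a response, where d is the number of responses that day and n the number still at risk. Each censored child's weight is passed to children observed later. The result can therefore never fall below the crude share of responders, and it exceeds that share whenever a non-responder is censored before a later response in the same arm.

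**Worked example (constructed).** Take 20 children with 4 responders (crude 20%), first responding on Days 8, 15, 29 and 31. The 16 non-responders have Week 4 visits on Days 26 (2), 27 (3), 28 (3), 29 (4), 30 (2), 31 (1) and 32 (1).

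| Day | At risk | Factor |
|---|---|---|
| 8 | 20 | 19/20 |
| 15 | 19 | 18/19 |
| 29 | 10 | 9/10 |
| 31 | 3 | 2/3 |

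- Actual days: 1 − (19/20)(18/19)(9/10)(2/3) = 1 − 0.54 = 46%.
- All Week 4 assessments at Day 29: 1 − (19/20)(18/19)(16/18) = 20%, the crude share.
- Nominal days, with two non-responders withdrawn at Days 8 and 15: 1 − (19/20)(17/18)(14/16) = 21.5%.

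In this example visit scatter adds 26 points and two withdrawals add 1.5.

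**Simulation.** Assumptions not in the documents: visit days uniform over ±2, ±3 and ±3 days; first responses split 20/30/50% over Weeks 1/2/4; no dropout; the SAP 12.2 rates taken as rates of ever responding.

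| Ever responding | Mean final value, actual days | Nominal days |
|---|---|---|
| 20.93% | about 34% (median trial about 30%) | 21% |
| 14.63% | about 24% | 15% |
| 2.7% | about 5% | 3% |

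On the curve, the 1% minus vehicle gap is then about 34 − 5 = 29 points, against 20.93 − 2.7 = 18.2 points. In about 18% of simulated trials the 1% arm reaches a median although fewer than half responded.

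**Sensitivity, 20.93% arm.**
- Scatter of ±1 day: about 28%.
- Share of first responses falling at Week 4 varied from 20% to 100%: about 27% to 44%.
- No scatter, 7% dropout with last IGA at Week 1 or 2: about 22%, an excess of about 1 point.
- No scatter and no dropout: no excess.

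**Check of the remedy.** With visit scatter and 7% dropout, carrying all non-responders to a common day after the last visit (Day 43) gives 20.9% against a crude 20.9%.

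**The case against.** Several objections have force.

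- *Size.* The visit scatter and the timing of first responses are assumed, and a long upper tail pulls up the means. Examples can be built that look far worse: if the last child assessed is a responder, the curve goes to 100%. Such cases show the mechanism, not the expected size. This stands, so the range matters more than any single figure.
- *Contradiction.* A reader might infer that 10.1.8 contradicts the non-responder rule. It does not. SAP 6.3.1 and 6.5 confine that rule to incidence of success, and neither mentions time to response. The same children are handled in two ways without explanation, but no two passages conflict.
- *Withdrawals.* Censoring at last assessment is ordinary Kaplan-Meier practice and is valid if withdrawal is non-informative. Protocol 3.8.3.1 makes that doubtful, since spread of the treatment area beyond 40% of BSA ends treatment, but the effect is small at the planned rates.
- *Differential dropout.* A reader might infer that more withdrawals on vehicle drive a difference between arms. The cited phase 2 trial had adverse-event discontinuations of 18.9% on vehicle and 7.0% on 1%, but over 8 weeks and in patients aged 10 to 70. Even 18.9% dropout moves the vehicle curve by well under 1 point on nominal days, because few vehicle children respond later. The gap widens because the excess grows with the response rate.
- *Match with the success table.* Ever responding is not the same as success at Week 4, since a child may respond and relapse. The two need not agree even after correction.
- *Log-rank test and VRS.* No distortion of the log-rank p-value has been shown. SAP 10.1.9 uses parallel wording ("Subjects who have failed to achieve a response will be treated as censored on the day of the final VRS assessment"), but VRS is recorded up to twice daily and only to Day 7, so the Week 4 result does not carry over.
- *Stakes.* The primary endpoint is adverse events, SAP 6.6 sets no significance level, and the success rates have their own confidence intervals.

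**Conclusion.** The point holds in a limited form. As written, SAP 10.1.8 uses actual days, and scattered Week 4 visits then make the cumulative response and the time to half responding overstate the share of children who ever responded. Under the stated assumptions a true 21% appears as about 34% on average, and as about 28% with tighter scatter. The excess is zero if all children are assessed on the same nominal day and none withdraws. Withdrawal is a minor contributor.

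The documents do not support reading this as an internal contradiction, as a bias driven by vehicle dropout, or as a demonstrated error in the log-rank test or the VRS analysis. If nominal days were intended, the SAP does not say so. The analysis is supportive, so this is a change that should be made, not one on which the trial's conclusions depend.

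**What to change.** In SAP 10.1.8, state that event and censoring times are the nominal timepoints of Table 6.4-1 (Day 8, 15 or 29), with children censored at a timepoint counted as at risk for responses at that timepoint. All children assessed at Week 4 then share one risk set. Compute the log-rank test and the median from the same times.

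Also state how early withdrawals without response are handled. To align with the non-responder rule, keep them in the risk set through Week 4, or treat withdrawal as a competing event, and report separately the number still under observation. The final value then equals the share who ever responded. Add a sentence that this need not equal the Week 4 success rate.

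SAP 10.1.9 could use the nominal hours of Table 6.4-2 for consistency.

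The cost is SAP wording and a few lines of code. The IGA curves become three-step functions with lower final values, and if withdrawals are retained, the number at risk includes children no longer observed.

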10.1.9 Time to Response in VRS

The time to response in VRS (time to the first response in VRS in each subject) will be analyzed in the same manner as the time to response in IGA. Subjects with a VRS score of 0 (none) or 1 (mild) with an improvement by at least 1 grade from the baseline are defined as responders. The starting point is baseline. Subjects who have failed to achieve a response will be treated as censored on the day of the final VRS assessment.

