### 3.7.4.4 Verbal Rating Scale (VRS) for Pruritus

The investigator or subinvestigator will evaluate the pruritus intensity based on VRS. The subjects aged 7 to 14 years old will evaluate the pruritus intensity according to the following criteria. The subjects will record the level of pruritus and the time and date of evaluation in a pruritus diary.

0: None

1: Mild

2: Moderate

3: Severe

The investigator or subinvestigator will record details of the pruritus diary in the CRF. The pruritus diary will be kept as the source document. For subjects aged 2 to 6 years, this will not be evaluated.

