5.1 Definitions of Analysis Sets

5.1.1 Efficacy Set

The efficacy set consists of all subjects who have received the IMP at least once and whose efficacy data has been obtained after the start of IMP administration.

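### The VRS time-to-response analysis leaves any child with baseline VRS 0 at risk for a response that child cannot reach; if such children exist, the curves are capped and the nominal log-rank comparison loses power

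*SAP*

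**What the plan says.** Only the older children rate itch on the VRS. Protocol 3.7.4.4 states: "The subjects aged 7 to 14 years old will evaluate the pruritus intensity according to the following criteria", with grades 0 (none), 1 (mild), 2 (moderate) and 3 (severe).

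Protocol 7.4.2, item 6, sets the response rule as a score of 0 or 1 "with an improvement by at least 1 grade from the baseline are defined as responders", and plans Kaplan-Meier plots only. SAP 10.1.9 keeps the rule: "Subjects with a VRS score of 0 (none) or 1 (mild) with an improvement by at least 1 grade from the baseline". It then says that time to VRS response "will be analyzed in the same manner as the time to response in IGA". This brings in the outputs of SAP 10.1.8: the cumulative response curve, the number at risk, a median described as "the time until one half of the subjects have achieved a response", and a between-group test reported through "the p-value of the log-rank test comparing the vehicle group and each OPA-15406 group".

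On children without a response, SAP 10.1.9 says: "Subjects who have failed to achieve a response will be treated as censored on the day of the final VRS assessment".

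The analysis population for efficacy is defined in SAP 5.1.1: "The efficacy set consists of all subjects who have received the IMP at least once and whose efficacy data has been obtained after the start" (that is, once treatment has begun). It sets no condition on baseline VRS.

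**The concern.** A one-grade improvement is impossible from grade 0. For IGA the matching rule causes no difficulty: entry requires IGA 2 or 3, so every enrolled child can improve by two grades and reach 0 or 1. SAP 10.1.9 carries the IGA method over to VRS, where entry sets no floor.

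A child with baseline VRS 0 would sit in the denominator of the curve and in every log-rank risk set up to the censoring time, with no possibility of an event. At stake are three outputs that the SAP orders: the height of the cumulative response curve, the median time to response, and the sensitivity of the comparison of each OPA-15406 group with vehicle.

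**Working it through.** **1. Can such children be enrolled?** Nothing in the protocol prevents it.
- The inclusion criteria (3.4.2) ask for IGA 2 or 3 and 5-40% of body surface affected. None asks for itch, and neither does any exclusion criterion (3.4.3).
- Protocol 3.5.2 explains that IGA leaves subjective symptoms out.
- Appendix 1 needs three of four basic features, and pruritus is only one of the four. The diagnosis also describes the disease, not itch on the baseline day.
- Systemic antihistamines at a stable dose are allowed (4.1).

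**2. How many children contribute?** The target is 60, with at least 8 aged 2-6 (protocol 3.3.1). So at most 60 - 8 = 52 have VRS data, an average of 52/3 = 17.3 per arm. In an arm of 17, each child with baseline VRS 0 removes 1/17 = 5.9 points of attainable response.

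**3. The plan's own figures.** The documents give no design figure for VRS. The IGA probabilities in SAP 12.2 (96.2%, 88.3%, 71.5%, 60.6%) come out at 95.5%, 86.9%, 71.5% and 58.9% by exact binomial enumeration with 20 per arm. All are within 2 points, and none bears on this question.

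**4. Effect on the curve.** Let p0 be the share with baseline VRS 0 and F(t) the cumulative response among the others. If the VRS-0 children are followed to the end of the diary, the curve for all children is (1 - p0) × F(t), so its ceiling is 1 - p0: 95%, 90%, 80% and 70% at p0 = 5%, 10%, 20% and 30%.

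Example, with assumed values: vehicle response 30% by 168 hours, hazard ratio 3.
- Active arm, children with itch at baseline: F = 1 - 0.7³ = 65.7%.
- All children: 0.9 × 65.7% = 59.1% at p0 = 10%; 0.7 × 65.7% = 46.0% at p0 = 30%.

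**5. Effect on the median.** In the same example, with exponential times, the hourly rate is 3 × 0.3567/168 = 0.00637. The median solves (1 - p0)(1 - e^(-0.00637t)) = 0.5.
- p0 = 0: 0.693/0.00637 = 109 hours.
- p0 = 10%: 0.811/0.00637 = 127 hours.
- p0 = 20%: 0.981/0.00637 = 154 hours.
- p0 = 30%: the curve ends at 46.0%, so the expected median is not reached within the diary.

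**6. Effect on the log-rank test.** Simulation with 2000 runs per setting: 17 per arm, the planned VRS times (4, 8 and 12 hours, then every 12 hours to 168), exponential response times, no other dropout, VRS-0 children censored at 168 hours. The test was run with these children kept and again with them removed, at a nominal two-sided 0.05. The share, vehicle response, hazard ratio and test level are all assumptions. Entries are power in %, kept / restricted.

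| Vehicle response, HR | p0 5% | p0 10% | p0 20% | p0 30% |
|---|---|---|---|---|
| 30%, HR 2 | 24.0 / 24.6 | 22.5 / 23.3 | 18.2 / 19.3 | 16.2 / 18.9 |
| 30%, HR 3 | 53.0 / 55.2 | 49.4 / 53.0 | 44.2 / 49.9 | 35.2 / 43.4 |
| 50%, HR 2 | 32.1 / 34.2 | 29.2 / 33.0 | 24.4 / 29.2 | 17.4 / 26.2 |
| 50%, HR 3 | 68.0 / 72.5 | 60.2 / 69.2 | 49.6 / 65.0 | 39.0 / 58.6 |

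The loss from keeping them is about 1-5 points at 5%, 1-9 at 10%, 1-15 at 20% and 3-20 at 30%.

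With no treatment effect (HR 1, 50% response in both arms), the rejection rate was 4.8-5.3% with the children kept and 5.2-6.0% with them removed. Both are near the nominal 5%.

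**The case against.** Four objections have weight.

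**The premise is not established.** The documents do not say that any child will have baseline VRS 0. Active disease, the stopping of topical steroids and topical antihistamines before baseline, and the exclusion of children satisfied with their current treatment all make it less likely. This stands: the point is conditional, and with no such child there is no effect.

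**The test decides nothing.** SAP 6.6 sets no significance level, the primary endpoint is adverse events, the protocol planned only plots here, and the output list in SAP 16.2 names no time-to-response table. This also stands, and it keeps the point small. It does not remove it, because SAP 10.1.8 and 10.1.9 still order the p-value, the median and the number at risk.

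**The estimand is a choice.** Among all children aged 7-14, the curve correctly shows the share who reach the defined response. That is fair. But that reading mixes absence of benefit with absence of anything to improve.

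**The problem may be visible anyway.** Protocol 7.5 asks for baseline VRS by group. A minimum of 0 would show, though not necessarily how many children have it.

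A reader might also infer that an uneven split of VRS-0 children between arms would be mistaken for a treatment effect. At 17 per arm and p0 = 10%, the difference in their share does have a standard deviation of sqrt(2 × 0.1 × 0.9/17) = 0.103, about 10 points. But under random allocation this is part of the chance variation that the test allows for, and the simulated error rate stays near 5%. The documents do not support a claim of bias. Nor do they support reading 17 as a maximum per arm. The minimum of 8 younger children caps the total only, and protocol 3.6 leaves the minimisation details to a separate specification.

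**Conclusion.** The point holds in a conditional and modest form. As written, the plan keeps any child with baseline VRS 0 in the risk set for an event that the definition rules out. If such children exist, the response curve is understated relative to children who can respond, the median moves later or is not reached, and the comparison with vehicle is attenuated. The error is in the conservative direction.

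The size depends on a share that the documents do not give. At 5% the loss is small. The 15-point loss at a 20% share arises only with the most favourable assumed effect (vehicle response 50%, hazard ratio 3). At a hazard ratio of 2, power is low with or without the change. The ceiling of 1 minus the share also assumes follow-up to the end of the diary; earlier censoring loosens it. This is a cheap improvement to a secondary analysis with nominal p-values, and no main conclusion of the trial rests on it.

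**What to change.** Add one sentence to SAP 10.1.9: the VRS time-to-response analysis (curves, number at risk, log-rank test and median) includes only children with a baseline VRS of 1 or more, and the number excluded is reported for each arm.

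Baseline VRS is recorded before the first application, so selecting on it respects the randomised comparison. The SAP is to be finalised before database lock (SAP section 4), so the rule can be set while the data are still blinded.

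The cost is interpretive. The result then applies to children with itch at baseline, a slightly different set from the one used for change in VRS, and the text should say so. If no child has baseline VRS 0, the results are unchanged.
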